10.5 Statistical Analysis of Analysis Set

Safety assessments will be performed on the ITT analysis set. The mITT cohort will serve as the principal data analysis set for the primary, secondary and tertiary efficacy endpoints analyses. The primary and secondary efficacy assessments will also be performed on the per protocol (PP) and the ITT analysis sets to show consistency of study results.

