### **12.7. Study Analysis Populations**

#### **12.7.1. Intent-to-Treat (ITT) Population:**

The intent-to-treat (ITT) population will include all subjects aged 22 through 70 enrolled in the study as randomized. This population will include all subjects who receive at least one active/sham treatment.

 Neurolief Brain Innovation	MOOD: CLINICAL INVESTIGATION PLAN	Doc No.: CL-CIP-201 Rev: REV.3 / 09June2021 Pg. 74 of 92
--	--	--

According to the ITT principle all subjects will be analyzed in the treatment group as assigned by randomization.

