#### **12.7.2. Modified Intent-to-Treat (mITT) Population:**

The modified intent-to-treat (mITT) population will include all subjects from the ITT set enrolled in the study, who completed the minimal stimulation time required by the protocol and have no post randomization exclusion criteria. The mITT analysis set will be analyzed in the treatment group as treated.

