#### **12.7.5. Statistical Analysis of Analysis Sets**

Safety assessments will be performed on the ITT and mYITT analysis set.

The mITT cohort will serve as the principal data analysis set for the primary and secondary statistical evaluation of the efficacy endpoints. The primary, secondary and exploratory efficacy assessment will also be performed on the per protocol (PP) analysis set as a sensitivity analysis and to show consistency of study results. The primary and secondary efficacy analyses will also be performed on the mYITT analysis set.

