11.5.6 Safety Analyses

Descriptive statistics will be presented per study group for all safety parameters. The primary safety variable, the cumulative incidence (and 95% CI) of device related adverse events (AEs) throughout the study, will be presented in tabular format and will include incidence tables by severity.

Adverse event rates will be compared between the study groups with a Fisher's exact test.

Serious adverse events will be listed and discussed individually.

Treatment tolerability will be compared between the study groups. The number and percent of subjects who fail to complete the study and the number and percent of subjects who fail to complete the study because of Adverse Events will be presented as well.

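### Safety is tabulated by randomised arm across a study in which sham devices become active, omits the subjects under 22, and leaves as-treated grouping to the principal efficacy set

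*SAP*

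**What the plan says.** SAP 10.5 names one population for safety: "Safety assessments will be performed on the ITT analysis set". The protocol named two: "Safety assessments will be performed on the ITT and mYITT analysis set" (12.7.5). SAP 10.4 then withdraws mYITT from separate analysis because only two subjects were under 22, and excludes those two from the other sets. SAP section 1 gives the SAP precedence.

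The grouping rules come from the protocol. For ITT (12.7.1): "According to the ITT principle all subjects will be analyzed in the treatment group as assigned by randomization". ITT covers ages 22 to 70, and on exposure: "This population will include all subjects who receive at least one active/sham treatment". For mITT (12.7.2): "The mITT analysis set will be analyzed in the treatment group as treated".

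On efficacy, SAP 10.5 says "The mITT cohort will serve as the principal data analysis set for the primary, secondary and tertiary efficacy endpoints analyses", and adds that "The primary and secondary efficacy assessments will also be performed on the per protocol (PP) and the ITT analysis sets".

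SAP 11.5.6 defines the primary safety variable as the cumulative incidence of device-related events over the whole study, and says "Adverse event rates will be compared between the study groups with a Fisher's exact test". SAP 8.4 sets the safety window at up to 18 weeks after treatment starts. Protocol 6.3.2 and 9.1.5 convert sham devices to active at the end of the 8-week double-blind phase for subjects who continue.

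**The concern.** A safety table asks what the delivered stimulation does, so each event belongs with the mode in use when it began. An efficacy comparison draws its validity from randomisation, so its groups should be the assigned arms. On the protocol's definitions the plan does the opposite in each case, and neither document's available text defines a separate safety set.

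Three consequences follow, in descending order of certainty.

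- After week 8 nobody is on sham, but the sham column keeps accumulating events. The between-group test on whole-study data then partly compares active stimulation with delayed active stimulation.
- The two subjects under 22 contribute to no safety table.
- If any subject used a device of the wrong mode in the double-blind phase, that subject's events sit in the wrong safety column, and in mITT the subject moves across the randomised comparison.

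The first and third tend to make the device look more like sham on safety. For a pivotal study meant to support marketing applications, that is the wrong direction in which to be imprecise.

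**Working it through.** **1. Sets and grouping rules side by side**

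| Analysis | Set | Grouping | Source |
|---|---|---|---|
| Safety | ITT (22–70, at least one treatment) | as randomised | SAP 10.5; Protocol 12.7.1 |
| Principal efficacy | mITT | as treated | SAP 10.5; Protocol 12.7.2 |
| Supportive efficacy | ITT | as randomised | SAP 7, 10.5; Protocol 12.7.1 |
| Safety on mYITT (Protocol 12.7.5) | withdrawn | – | SAP 10.4, 10.5 |

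No as-treated safety table remains under the SAP. An as-randomised efficacy analysis remains, but only as support.

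**2. Arm size**

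The documents give no adverse event rates and no count of mismatched devices, so there is no planned safety figure to reproduce. The arm size comes from Protocol 12.4: 106/0.85 = 124.7, stated as 124. At 1:1 that is 62 per arm. All rates below are assumptions.

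**3. Effect of the open-label conversion**

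Let p be the risk of a first device-related event in the first 8 weeks on active, q the risk in 8 weeks on sham, and r the risk of a first event in the second 8 weeks on active. Assume that everyone continues and that converted sham subjects have risk p in their first 8 active weeks.

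- Cumulative, active arm: 1 − (1 − p)(1 − r)
- Cumulative, sham arm: 1 − (1 − q)(1 − p)
- Cumulative difference: (1 − p)(r − q), against a double-blind difference of p − q

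| p, q | Double-blind difference | r = p | r = p/2 | r = 0 |
|---|---|---|---|---|
| 0.30, 0.10 | 20 points | 0.70 × 0.20 = 14.0 | 0.70 × 0.05 = 3.5 | 0.70 × (−0.10) = −7.0 |
| 0.20, 0.05 | 15 points | 0.80 × 0.15 = 12.0 | 0.80 × 0.05 = 4.0 | 0.80 × (−0.05) = −4.0 |

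For r = p/2 in the first row the arms are 40.5% and 37.0%; in the second, 28.0% and 24.0%. When p exceeds q and r is no larger than p, the cumulative difference is always smaller than p − q, and it reverses if r falls below q. Full continuation is the extreme case. Protocol 9.1.5 ends participation for non-compliant subjects, so the true effect would be smaller. Open-label regimens also differ by response (Protocol 6.3.2), so r and the risk after conversion may depart from these values.

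**4. Effect of a double-blind mode mismatch, if one occurred**

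Take one sham-assigned subject who used an active device and had an event. Moving only the event over fixed denominators shifts each arm by 1/62 = 1.6 points, or 2/62 = 3.2 points in the difference. Regrouping moves the whole subject, so the shift is (1 − p_active)/63 + (1 − p_sham)/61.

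- At 19/62 active and 6/62 sham: 19/62 = 30.6% becomes 20/63 = 31.7%, and 6/62 = 9.7% becomes 5/61 = 8.2%. The shift is 1.10 + 1.48 = 2.6 points.
- At 12/62 and 3/62: 13/63 and 2/61, a shift of 2.8 points.

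So 3.2 points is the limit as both rates approach zero.

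Averaged over subjects with and without events, k mismatches in each arm multiply the true difference by 1 − 2k/62. From 20.0 points that gives 19.4 (k = 1), 18.1 (k = 3) and 16.8 (k = 5). At k = 0 nothing changes.

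**The case against.** The best reply starts with the missing text. SAP 10.1 to 10.3, which would define ITT, mITT and PP, were not available to this review, and the SAP prevails over the protocol. The ITT and mITT rules used here are the protocol's. The SAP's available mYITT definition repeats the protocol's as-treated wording, which supports the inference for mITT but says nothing about ITT. This stands as a condition on the finding.

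Second, a reader might infer that events on wrong or replaced devices are in fact being counted against the other arm. The documents do not support that. The randomisation scheme ties each serial number to a subject (Protocol 6.5.2), shipment follows assignment (6.10), replaced devices are recorded (6.12), and replacement rules sit in a separate plan that was not available (6.11). A same-mode replacement moves nothing, and no mismatch is reported. The week-8 conversion is also a planned step and not a misallocation; it matters because of how events are cumulated.

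Third, a reader might infer that safety is tabulated twice under opposite grouping rules. That was true of the protocol, but the SAP has withdrawn mYITT.

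Fourth, it would be too strong to say that events are hidden. Relatedness is assessed for each event, related events are adjudicated (Protocol 11.3.7), and serious events are listed individually. Misattribution changes an event's column and does not remove it.

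Fifth, ITT already requires exposure, so for ages 22 to 70 it has the membership of a safety set, and a competent programmer may split the tables by phase unprompted. Both are fair, but the plan does not call for the split, and its open-label section (SAP 11.5.7) contains no adverse event analysis.

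**Conclusion.** The point holds, as a minor one that is cheap to correct. On the protocol's definitions, safety is grouped as randomised and principal efficacy as treated, and the two subjects under 22 are in no safety table. The SAP does not say whether both of them took a treatment.

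The part that needs no error in conduct is the open-label one: any continuing sham subject with a first device-related event after conversion is counted under sham. Its size is unknown because the documents give no event rates. Under the assumed rates and full continuation, a 20-point double-blind difference becomes anything from 14.0 to −7.0 points, depending on how far risk falls in the second 8 weeks on active stimulation.

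The mismatch part is conditional. It is zero if no mismatch occurred, and otherwise at most about 3.2 points per mismatched subject with an event (about 2.6 at 19/62 and 6/62). The same condition governs any harm to efficacy from as-treated grouping in mITT. Nothing here changes the sample size.

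**What to change.** In SAP 10.5, define a safety set of all subjects with at least one treatment, including those under 22, grouped by the mode actually delivered. State that efficacy is grouped as randomised in every analysis set. List any device mismatches.

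In SAP 11.5.6, tabulate adverse events by phase and by mode in use at onset, and limit the active-sham Fisher test to the double-blind phase. Grouping by double-blind mode alone would not be enough, because open-label events of converted subjects would still fall under sham.

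The cost is a few sentences and some extra table columns. Serial numbers and dispensing are already recorded (Protocol 6.10, 6.12), event start dates are collected (11.3.1), and the conversion day marks the first day of the open-label phase (9.1.5), so mode at onset can be derived without new data. SAP section 6 says that the treatment code had not been revealed when the SAP was finalised. If it has been revealed since, the change should be reported as a deviation with its reason, as SAP 11.1 provides.

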11. STATISTICAL ANALYSIS

11.1 General Considerations

Statistical analyses will be performed using SAS® v9.4 (SAS Institute, Cary NC, USA). Statistical analyses and reporting will be performed in compliance with FDA Guidance 21 CFR part 812 and E9, ISO 14155, and MDR 2017/745. Study data will be summarized with descriptive statistics and presented in tables and figures. Continuous variables will be summarized by a mean, standard deviation, minimum, median and maximum and categorical variables by a count and percentage. For comparison of means (continuous variables), the two-sample t-test or the Wilcoxon rank sum test will be used as appropriate. For comparison of proportions (categorical variables), the chi-squared test or Fisher's exact test will be used as appropriate. If multiple measurements are taken in a single subject, statistics described below will be appropriately modified to accommodate the

within subject correlation Deviations from the planned analysis will be described, with proper justification, in the clinical study report.

11.2 Demographic and Case Characteristics

Demographic and baseline condition related characteristics will be tabulated and compared between the study groups by data type. Continuous variables will be summarized by a mean, standard deviation, minimum, median and maximum and categorical variables by a count and percentage. The statistical evaluation of baseline characteristics will include all available data from the ITT population.

These data will include:

- Demographic data
- Medical history
- Psychiatric history
- Previous and Current Psychotropic Medication and/or other treatments (i.e. psychotherapy, other medical devices)
- Type, dose and frequency of concomitant medications

11.3 Disposition and Subject Tolerability

The number of subjects who entered the study and completed each stage of the study will be provided and compared between the study groups, as well as the reasons for all post randomization discontinuations, grouped by major reason, e.g., lost to follow-up, adverse event, poor compliance, did not administer any treatment (with reasons). A list of discontinued patients, protocol deviations and subjects excluded from the efficacy analysis will be provided as well.

Time to withdrawal will also be assessed and presented by Kaplan-Meier curves and will be compared using the Log-Rank test if relevant.

11.4 Prognostic Factor Analysis

This section is intended to provide the architecture for this evaluation and does not jeopardize the sanctity of this study because this evaluation is being conducted independent of the randomized treatment assignment. Although

randomization creates asymptotic balance in important prognostic factors, including baseline values of the outcome variable in finite samples an imbalance in such factors may occur notwithstanding randomization, this represents the difference between the expectation of a random process and its realization. Depending crucially on the correlation between the baseline covariate and the outcome variable, this chance imbalance may not only create a potential bias in crude estimates of treatment effect in the outcome variable but may also affect the precision with which such an effect is measured and the statistical power of the analysis. Adjustment through the ANCOVA model is recommended to reduce risk of bias whilst also improving the precision of estimates and the power of the statistical test (Egbewale et al. BMC Medical Research Methodology 2014, 14:49). Specifically, if there was a significant difference in the HDRS-17 or in the secondary endpoints response and remission rates detected between the active and sham groups at 8 weeks post treatment initiation, but a retrospective analysis determined that the effect may have been influenced by one or more covariates not defined in the randomization scheme, the conclusion drawn from the unadjusted results could be challenged (Egbewale et al. BMC Medical Research Methodology 2014, 14:49).

The protocol and Statistical Analysis Plan (SAP) are clear regarding the tests for poolability (12.9.6 of the study protocol) and subset analyses (12.9.1 of the study protocol) that should be conducted. From Section 12.9.6 of the study protocol:

"Subgroup analysis of the primary efficacy endpoint by comparing US vs OUS centers, will be used to evaluate the poolability of the results. Treatment by center interaction will be tested in the primary analysis model at a significance level of 10%. If the interaction is not significant, it will be removed from the model. If the interaction is found significant, it will also be removed from the model and the reason for this interaction will be further explored and rationalized. This evaluation may include demographic features, symptoms at presentation, and clinical and treatment history, and center comparability in the features found to be associated with the primary efficacy variable.

In the case that poolability is questionable, the reasons for differential treatment effect, such as subject and clinical characteristics, will be investigated and reported.”

From Section 12.9.1 of the study protocol:

“Subset Analyses of Primary Endpoint:

Significant or important variables, such as demographic or other baseline patient characteristics or concomitant medications (depending on use), will be entered as additional covariates in the primary efficacy endpoint ANCOVA model to evaluate their effect on the change from baseline HDRS-17 score.

- *Use of concomitant medications .*
- *US vs. OUS sites*
- *Blinding assessment - The effect of potential unblinding will be evaluated as a sensitivity analysis, where an additional binary variable identifying subjects unblinded versus those not un-blinded will be added to the ANCOVA model as a covariate. “*

The prognostic factor analysis is an extension of the examination of poolability and subsets, with an important difference not addressed in sections 11.5.2 and 11.5.3 of the SAP. Specifically, that the list of factors that may play a role in response have been prospectively defined and a threshold for inclusion has been defined. Before the final analysis is conducted on the locked data, the baseline factors will be examined using the locked database and significant covariates may be incorporated into the final model for analysis if deemed appropriate.

The following factors will be tested:

- Age.
- Sex at Birth
- Years of education.
- Employment status.
- ATRF score.
- ATIF score.
- Age of first episode.
- # of episodes since initial diagnosis.

- Other device use yes/no.
- Duration of other device used.
- Current episode duration.
- Psychotherapy yes/no.
- Duration of Psychotherapy.
- Each HDRS 17/21 item separately at baseline.
- Total HDRS 17/21 scores at baseline.
- Each separate MADRS item at baseline.
- Total MADRS scores at baseline.
- Baseline CGI-S scores.
- Baseline C-SSRS score Lifetime/ past 12 months.
- Baseline QIDS-16 score.

To assess correlation of the listed variables with the primary efficacy endpoint change from baseline HDRS-17 score to week 8 an ANOVA model will be used, entering each variable univariately as the independent variable. The same will be done for change from baseline HDRS-17 score to week 4.

To assess correlation of the listed variables for the binary variables (response and remission) a logistic regression model will be used, entering each variable univariately as the independent variable. The same will be done for change from baseline HDRS-17 score to week 4.

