### 12.2. Study Endpoint Variables

#### 12.2.1. Primary endpoint variable

The primary endpoint is the change in HDRS17 total score from baseline to 8 weeks post treatment initiation, in each of the study groups. This variable will be calculated by subtracting the subject's baseline HDRS17 score from the score at visit 4.

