We use conservative estimates of a 3.3-point difference with a standard deviation of 6 points. Calculations show that a sample size of 53 subjects per group (total 106) would provide 80% power at a 5% level of significance (two-sided) to detect the difference between treatment and sham groups.

Given our preliminary results, together with other companies clinically relevant data, we hypothesize that our statistical assumptions are aligned with competitive treatments for MDD.

The company anticipates that after randomization, but before the endpoint can be observed, up to 15% of the subjects will drop out from the study irrespective of study arm and success of treatment; thus, an adjustment for this drop-out rate is made and a sample size of 124 is required at the point of randomization.

We shall randomize an additional up to 36 subjects (30+15% dropout) in the age range 18-21 to assess efficacy in this age range as well.

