11.5 Endpoints Analyses

11.5.1 Primary Efficacy Endpoint Analyses

The primary efficacy endpoint is the change from baseline to 8 weeks post treatment initiation in HDRS-17 score.

The change in HDRS-17 from baseline to 8 weeks post treatment initiation will be compared between the treatment groups using a repeated measures analysis of covariance (ANCOVA, SAS® MIXED procedure). The model will include the following fixed effects: treatment group, visit, treatment group by visit interaction

with Baseline HDRS-17, and center entered as covariates. If covariates are identified in the prognostic factor analysis, they may be added to the model as well. Baseline HDRS-17 scores will be entered as a continuous variable so that the potential for co-linearity problems will be minimized. The treatment group by center interaction will be evaluated as well, but not as part of the principal statistical evaluation.

The unstructured covariance matrix structure will be used. If the model does not converge, then either the compound symmetry or autoregressive (whichever model has the lower AIC statistic) covariance matrix structure will be used instead. At this time point (up to 8 weeks) we do not expect a high proportion of dropouts, as a placebo effect of the sham treatment is expected and was taken into consideration in the design of the study. Thus, any missing data at 8 weeks post treatment initiation can be considered missing at random. Therefore, since repeated measures ANOVA is also an imputation method, for this evaluation no other method of imputation of missing data is considered beyond the model estimates. Nevertheless, should the missing at random assumption prove to be incorrect, a sensitivity analysis using other methods for data imputation mentioned in Section 7 may be performed.

Mock SAS code for the analysis:

```
Proc Mixed data=HDRS17;
  class visit group center subjectid;
  model change_HDRS17 = baseline_HDRS17 visit group visit*group;
  repeated / type=un subject=subjectid;
  lsmeans group*visit / pdiff cl;
  random center;
run;
```

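### The prognostic screen in SAP 11.4 relates each factor to HDRS-17 change without baseline HDRS-17, so it tests a different association from the one the baseline-adjusted primary model can use

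*SAP*

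**What the plan says.** SAP 11.4 lists the candidate factors. They include demographic and history items and many baseline severity measures: "Each HDRS 17/21 item separately at baseline", the HDRS totals, every MADRS item and the MADRS total, CGI-S, C-SSRS and QIDS. For the primary endpoint, change in "HDRS-17 score to week 8 an ANOVA model will be used, entering each variable univariately as the independent variable"; the same is planned for week 4. Response and remission are screened by univariate logistic regression. Nothing in the section puts baseline HDRS-17 into a screening model. The baseline total is itself only one of the candidates.

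Protocol 12.2.1 computes the outcome by subtracting the "baseline HDRS17 score from the score at visit 4", so baseline sits inside it with coefficient −1. The mock code in SAP 11.5.1 has "model change_HDRS17 = baseline_HDRS17 visit group visit*group", so baseline is already a covariate there.

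The screen feeds that model by option. SAP 11.4 says "significant covariates may be incorporated into the final model for analysis if deemed appropriate" and SAP 11.5.1 says "If covariates are identified in the prognostic factor analysis, they may be added to the model as well". SAP 11.4 also states that "a threshold for inclusion has been defined", but the text gives no value.

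**The concern.** SAP 11.4 justifies covariate adjustment partly by better precision and power. In a model that already holds baseline HDRS-17, an added factor improves precision only through its relation with outcome given baseline. The screen tests its marginal relation with change. The two differ for any factor correlated with baseline HDRS-17, and much of the candidate list is such factors; the HDRS-17 items are components of the subtracted score.

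Two errors follow when the week-8-on-baseline slope is below 1. A severity score with nothing to add looks prognostic because patients with high baselines tend to fall further. And a factor that goes with higher baseline and also with a worse outcome given baseline has two effects on change that offset each other, so it can escape notice. At stake are the choice of optional covariates for a pivotal analysis and the reported list of prognostic factors. The screen would have this defect even if every choice were fixed in advance and made blind.

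**Working it through.** **1. The plan's own figure.** Protocol 12.4: "We use conservative estimates of a 3.3-point difference with a standard deviation of 6 points". A two-sided 5% t-test with 53 per group gives 80.1% power (52 per group gives 79.3%), so 53 per group, 106 in total, is reproduced. N = 106 and change SD 6 are used below.

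**2. Assumptions not in the documents.** Baseline HDRS-17 SD (SD_B) 2.5–4; slope b of week-8 score on baseline 0.3–0.7; screening threshold 0.05. As a rough guide to b only: Protocol 12.4 cites mean reductions of 40.7% (active) and 30.9% (placebo). If improvement were proportional to baseline, b would be 1 − 0.407 = 0.59 to 1 − 0.309 = 0.69.

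**3. What the screen sees.** Let B be baseline, X a standardized factor with correlation r with B, and g the effect of X on the week-8 score given baseline. Then

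change = (b − 1)B + gX + error, with SD 6, and corr(X, change) = [r(b − 1)SD_B + g] / 6.

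The rejection probability is close to Φ(|z| − 1.96) + Φ(−|z| − 1.96), where z = atanh(corr) × √103.

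- Redundant score (g = 0), r = 0.8, SD_B = 4, b = 0.3: corr = 0.8 × (−0.7) × 4 / 6 = −0.373, |z| = 3.98, selected 98%.
- Redundant score, r = 0.8, SD_B = 2.5, b = 0.7: corr = −0.10, |z| = 1.02, selected 17–18%.
- Masked factor (g = 1.8, r = 0.5), SD_B = 4, b = 0.3: corr = (−1.4 + 1.8) / 6 = 0.067, z = 0.68, found 10%.
- Masked factor, SD_B = 2.5, b = 0.7: corr = (−0.375 + 1.8) / 6 = 0.2375, z = 2.46, found 69%.

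**4. Simulation, 20,000 trials per cell.**

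| SD_B, b | Redundant, r = 0.25 | Redundant, r = 0.8 | Masked, as planned | Masked, adjusted |
|---|---|---|---|---|
| 2.5, 0.7 | 6% | 18% | 69% | 77% |
| 3, 0.5 | 10% | 54% | 43% | 77% |
| 4, 0.5 | 14% | 79% | 28% | 79% |
| 4, 0.3 | 22% | 98% | 10% | 81% |

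With baseline in the screening model, redundant scores are selected about 5% of the time in every cell. At b = 1 the unadjusted rate is also 5%, so there is no artefact. At the rough-guide slopes (0.59–0.69, SD_B 3–4), redundant scores are selected 7–10% (r = 0.25) and 25–62% (r = 0.8); the masked factor is found 40–62%, against 76–78% adjusted.

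**5. Where the screen works.** For a factor with partial correlation 0.3 given baseline, SD_B = 4 and b = 0.6: found 86% as planned against 88% adjusted if uncorrelated with baseline, and 97% against 88% if its correlation with baseline is −0.3.

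**6. Cost to the primary test** (SD_B = 4, b = 0.6, 53 per group). Residual SD = √(36 − (0.4 × 4)²) = 5.78; power 82.9%. Adding the factor with partial correlation 0.3: 5.78 × √(1 − 0.09) = 5.52; power 86.2%. Missing it therefore costs 86.2 − 82.9 = 3.3 points. One to five redundant scores leave 82.9% on degrees of freedom alone. Simulating chance imbalance in the added scores as well takes off at most two or three points at five. Ten or twenty redundant scores cost more: 77% and 71%, in a run that starts at about 81%.

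**The case against.** The strongest reply is that the screen need not serve the primary model. The SAP introduction describes it as identifying baseline parameters related to the primary endpoint and its derivatives. The endpoint is change, so a univariate relation with change answers that descriptive question. Entry into the model is optional, and a statistician can decline a score that duplicates baseline HDRS-17. Age group, sex and ATRF group are examined in the baseline-adjusted ANCOVA anyway (SAP 11.5.2). The entry criterion of HDRS21 at least 20 truncates baseline, which favors the smaller figures.

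Much of this stands. It rules out saying that every severity score will be selected, or that useful factors are missed in general: step 5 shows that factors unrelated to baseline lose almost nothing and some are found more often. It also keeps the cost small. What does not stand is the idea that discretion repairs the screen, because no rule removes redundant scores and a factor that was never flagged will not be considered. The subset analyses are a separate evaluation and omit the items, MADRS, CGI-S, C-SSRS and QIDS.

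A reader might infer that the treatment estimate is biased. The documents do not support that: baseline HDRS-17 stays in the primary model, and SAP 11.4 describes the screen as independent of treatment assignment. A reader might also carry the argument over to the binary endpoints. Remission is a score threshold at week 8, not a change score, and the response and remission analyses in SAP 11.5.4 contain no baseline HDRS-17, so the baseline total is not redundant there.

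**Conclusion.** The point holds as a limited one. For choosing covariates for the primary ANCOVA, the HDRS-17 change screen tests the wrong association. The error rates in steps 3 and 4 depend on a baseline SD, a slope and a threshold that the documents do not give; they shrink as the slope approaches 1 and vanish there. The missed factors are those whose effect given baseline runs against their overlap with baseline. The consequence is a misleading list of prognostic factors and a small loss of efficiency, about 3 power points for each missed factor with partial correlation 0.3 and little or nothing for a few redundant ones. It is worth correcting mainly because the correction is so cheap.

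**What to change.** In SAP 11.4, for both the week-8 and week-4 HDRS-17 change screens, fit change = baseline HDRS-17 + center + factor and select on the factor's partial association. State the threshold. Do not count baseline HDRS-17 total as a candidate for the primary model, which already has it.

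For response and remission, keep the baseline total available. Either leave it on the candidate list, or put it in both the logistic screens and the adjusted logistic models of SAP 11.5.4. Removing it from the list outright would close its only route into those models.

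The cost is SAP wording and extra terms (baseline HDRS-17, with center as in the primary model) in each change screen, with no new data. Factors that overlap with baseline in the same direction as their effect will be selected somewhat less often (88% against 97% in step 5).
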